5.4.4 Management of Infusion Reactions Associated with Pembrolizumab

Signs and symptoms usually develop during or shortly after pembrolizumab infusion and generally resolve completely within 24 hours of completion of infusion. Table 9 shows treatment guidelines for subjects who experience an infusion reaction associated with administration of pembrolizumab. The Study Medical Monitor will be consulted regarding continued dosing of CRS-207 and/or epacadostat should any of the events listed in Table 9 occur.

Table 9 Pembrolizumab Infusion Reaction Treatment Guidelines

NCI CTCAE Grade	Treatment	Premedication at subsequent dosing
Grade 1 Mild reaction; infusion interruption not indicated; intervention not indicated	Increase monitoring of vital signs as medically indicated until the subject is deemed medically stable in the opinion of the investigator.	None
Grade 2 Requires infusion interruption but responds promptly to symptomatic treatment (e.g., antihistamines, NSAIDS, narcotics, IV fluids); prophylactic medications indicated for < =24 hrs	Stop Infusion and monitor symptoms. Additional appropriate medical therapy may include but is not limited to: IV fluids Antihistamines NSAIDS Acetaminophen Narcotics Increase monitoring of vital signs as medically indicated until the subject is deemed medically stable in the opinion of the investigator. If symptoms resolve within one hour of stopping drug infusion, the infusion may be restarted at 50% of the original infusion rate (e.g., from 100 mL/hr to 50 mL/hr). Otherwise dosing will be held until symptoms resolve and the subject should be premedicated for the next scheduled dose. Subjects who develop Grade 2 toxicity despite adequate premedication should be permanently discontinued from further trial treatment administration.	Subject may be premedicated 1.5h (± 30 minutes) prior to infusion of pembrolizumab (MK-3475) with: Diphenhydramine 50 mg po (or equivalent dose of antihistamine). Acetaminophen 500-1000 mg po (or equivalent dose of antipyretic).
Grades 3 or 4 Grade 3: Prolonged (i.e. not rapidly responsive to symptomatic medication and/or brief interruption of infusion); recurrence of symptoms following initial improvement; hospitalization indicated for other clinical sequelae (e.g., renal impairment, pulmonary infiltrates) Grade 4: Life-threatening; pressor or ventilatory support indicated	Stop Infusion. Additional appropriate medical therapy may include but is not limited to: IV fluids Antihistamines NSAIDS Acetaminophen Narcotics Oxygen Pressors Corticosteroids Epinephrine Increase monitoring of vital signs as medically indicated until the subject is deemed medically stable in the opinion of the investigator. Hospitalization may be indicated. Subject is permanently discontinued from further trial treatment administration.	No subsequent dosing
Appropriate resuscitation equipment should be available in the room and a physician readily available during the period of drug administration.		

5.4.5 Supportive Care

Subjects should receive appropriate supportive care measures as deemed necessary by the treating Investigator, including, but not limited to, the items outlined below:

- Nausea/vomiting: nausea and vomiting should be treated aggressively, and prophylactic antiemetic therapy should be used according to standard institutional practice. If a subject requires daily administration of an antiemetic, an alternative to dexamethasone should be used. Subjects should be strongly encouraged to maintain liberal oral fluid intake.

5.4.6 Procedures for Subjects Exhibiting Serotonin Syndrome

As noted in [Section 1.3.4](#), there is a theoretical chance that epacadostat could cause an increase in serotonin levels in the brain that might trigger SS when administered in combination with other serotonergic agents.⁶⁰ This syndrome has been most closely associated with use of MAOIs, Demerol[®], linezolid, or methylene blue; all of these agents are prohibited during the study (see [Appendix D](#) for prohibited medications associated with MAO inhibition). SSRIs and serotonin/norepinephrine reuptake inhibitors (SNRIs) are permitted in the study. Subjects will be provided with an informative subject leaflet describing the signs and symptoms of the syndrome along with instructions to seek immediate medical care if any of these signs or symptoms are observed. The following procedures will be implemented if subjects exhibit the signs/symptoms of SS described in Table 10, including tremor; hyperreflexia; and spontaneous, ocular, or inducible clonus, together with agitation, fever, diaphoresis, or muscle rigidity:

- Immediately interrupt all study drug administration;
- Immediately interrupt any SSRI or SNRI administration;
- Provide appropriate medical management of the subject until all signs/symptoms are resolved (e.g. IV fluids and/or sympathomimetic amines for hypotension, benzodiazepines for agitation, administration of 5-hydroxytryptamine antagonists such as cyproheptadine);
- If subject chooses to remain in the study, restart treatment with epacadostat after the SSRI or SNRI has been discontinued, no sooner than 5 half-lives have elapsed for the specific SSRI or SNRI in question, and after resolution of signs/symptoms of SS. The SSRI or SNRI treatment MAY NOT be restarted; and
- If subject chooses to withdraw from the study or must restart treatment with SSRI or SNRI, the subject should be scheduled for a follow-up visit. Treatment with SSRI or SNRI may be initiated 2 weeks after resolution of signs and symptoms of SS.

Table 10 Signs and Symptoms of Serotonin Syndrome

Tremor and hyperreflexia
Spontaneous clonus
Muscle rigidity, temperature >38°C (100.4°F), and either ocular clonus or inducible clonus
Ocular clonus and either agitation or diaphoresis
Inducible clonus and either agitation or diaphoresis

5.5 Drug Supplies

5.5.1 Formulation, Packaging, Preparation, and Dispensing

5.5.1.1 CRS-207

CRS-207 is a formulated live-attenuated strain hMeso38 of *Lm*, derived by deletion of *actA* and *inlB* coding sequences from a Streptomycin-resistant, wild-type strain and insertion of the hMeso coding sequence. The CRS-207 drug product consists of attenuated *Lm* (1×10^9 CFU total)

suspended in [REDACTED]. The drug product is filled at a volume of 1.5 mL into a single-use 2R injection glass vials with a gray butyl stopper and aluminum crimp seal with a flip-off cap, and stored frozen at -60°C or colder until IV administration. CRS-207 is supplied by Aduro Biotech.

5.5.1.2 Epacadostat

Epacadostat (INCB024360) is formulated as an immediate release tablet. For this study, 25 mg and 100 mg tablets will be available. [REDACTED]

[REDACTED]

Epacadostat will be packaged in high-density polyethylene bottles of 35 tablets. Bottles will be labeled in the local language, and will comply with the legal and regulatory requirements of each country.

Epacadostat tablets will be dispensed on Day 1 of each indicated cycle in a sufficient amount required for the period of time until the next visit. Subjects will be provided a dosing diary and instructed to record each study drug dosing. Subjects will be instructed to return all unused study drug at the next visit.

Epacadostat is supplied by Incyte Corporation.

5.5.1.3 Pembrolizumab

Pembrolizumab, a humanized monoclonal antibody, is formulated and supplied as either a lyophilized powder or solution.

Pembrolizumab for injection is a sterile, preservative-free, white to off-white lyophilized powder in single-use vials. Each vial is reconstituted and diluted for intravenous infusion. Each 2 mL of reconstituted solution contains 50 mg of pembrolizumab and is formulated in L-histidine (3.1 mg), polysorbate 80 (0.4 mg), and sucrose (140 mg). May contain hydrochloric acid/sodium hydroxide to adjust pH to 5.5.

Pembrolizumab for injection is a sterile, preservative-free, clear to slightly opalescent, colorless to slightly yellow solution that requires dilution for IV infusion. Each vial contains 100 mg of pembrolizumab in 4 mL of solution. Each 1 mL of solution contains 25 mg of pembrolizumab and is formulated in: L-histidine (1.55 mg), polysorbate 80 (0.2 mg), sucrose (70 mg), and Water for Injection, USP.

5.5.2 Study Drug Administration

5.5.2.1 CRS-207

CRS-207 is intended for administration by IV infusion (no in-line IV filter should be used). Additional details for storage and preparation of CRS-207 are provided in the study Pharmacy Manual.

Use of Central Lines:

To avoid contamination of a central line (e.g. infusion ports, peripherally inserted central catheter lines) with CRS-207 during and after infusion:

- **CRS-207 must NOT be administered through a central line or infusion ports;**
- **Central lines must NOT be used or accessed for any reason once the CRS-207 infusion has been initiated (including blood draws, medication administration, or line flushing; blood draws prior to infusion through a port or central line are allowed) and through 4 days after infusion;**
- **Central lines must be clearly labeled with tape or other method indicating the date when the port may be used again after CRS-207 infusion.**

Pre-Medication and Post-Infusion Observation

Before each CRS-207 infusion, subjects should be pre-medicated with 650 mg (or the maximum dose permitted by label) acetaminophen (paracetamol). Subjects allergic to acetaminophen may receive 800 mg ibuprofen. All subjects are required to receive a minimum of 500 mL of normal saline immediately before CRS-207 infusion; an additional 0.5 - 1 L after infusion is recommended, as tolerated. Additional fluids may be given for persistent tachycardia, fever, or hypotension based on Investigator's discretion.

Subjects will be observed in the clinic for at least 4 hours after the first CRS-207 infusion and at least 2 hours following each subsequent infusion. Subjects should continue to be monitored after infusion and released once they are considered clinically stable. Vital signs (blood pressure [BP], pulse, respiratory rate, temperature) will be obtained every 30 minutes during the CRS-207 infusion and every hour during post-infusion follow-up. Presence of fever alone does not preclude the subject from being released. Hospital admissions for overnight monitoring will not be considered an SAE unless the event meets criteria for seriousness other than hospitalization.

Accumulating subject experience during and after CRS-207 infusions at 1×10^9 CFU has further demonstrated the following clinical observations, which are to be expected:

- **Fevers:** Despite the acetaminophen premedication, subjects can spike fevers up to 40°C starting at the end of the CRS-207 infusion generally through the next 24 hours. Oral ibuprofen (400 to 800 mg) and acetaminophen (650 to 1000 mg) can be used in alternate sequence every 4 hours. Rarely, a cooling blanket has been used during the clinic stay. Fevers after 24 hours are uncommon and rare after 36 hours.
- **Rigors:** Rigors/chills have been observed starting during or at the end of the CRS-207 infusion through 24 hours. IV narcotics such as morphine (use of meperidine is prohibited per protocol) can be administered per institutional policy.

- **BP:** Small drops in BP have been observed necessitating additional IV fluids during the 4 hour observation period (up to 1 or 2 L). Reasons for this include the development of may experience fever, compartmental shifts of fluid resulting from the CRS-207 infusion, and the use of narcotics. Some subjects have also been slightly hypotensive at 24 hours upon arrival to the clinic on Day 2. Subjects are encouraged to hydrate themselves liberally at home with oral fluids.
- **Appetite:** Appetite is generally suppressed during the 24 hours after CRS-207 infusion related to the factors listed above. Liberal intake of fluids is encouraged.
- **Nausea** and vomiting: Nausea and vomiting have been reported and observed infrequently within 24 hours after CRS-207 infusion.

For more information, Refer to [Section 5.6.1](#) and the IB for additional details on CRS-207 administration and supportive care.

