Epacadostat ²⁴				X	← BID →																		
Epacadostat Compliance & Accountability ²⁵				X	X	X	X	X	X	X	X	X	X	X	X	X	X	X	X				
Other Concomitant Medication																							
Antibiotics ²⁶																			X				

Footnotes

1. **Treatment** will continue for as long as there is potential for clinical benefit except that pembrolizumab will continue for a maximum of 24 months. At Cycle 5 and beyond, additional clinic visits between administrations of pembrolizumab and CRS-207 will be conducted based on Investigator's discretion and clinical indication.
2. **EOT Visit** will occur as soon as determined that the subject will permanently discontinue study treatment, and at least 7 days after the last dose of CRS-207. If the EOT visit coincides with a regular study visit, the EOT evaluations will supersede those of that scheduled visit, and the data should be entered in the EOT page in the eCRF. If the EOT Visit occurs >21 days after the last administration of study drug, procedures from the EOT and Safety Follow-up visits may be collected as a single Safety Follow-up Visit.
3. **Safety Follow-up Visit** will be scheduled 30 days (+5 days) post last dose of study treatment. If the subject begins another anticancer therapy before the Safety Follow-up Visit, every effort will be made to complete all of the Safety Follow-up Visit assessments prior to commencing the new therapy. If there is an adverse event in need of monitoring beyond the Safety Follow-up Visit, the subject will be followed until resolution or confirmed stability of the adverse event. If a CT scan was collected within 9 weeks (± 7 days) of the Safety Follow-up Visit, then a CT scan at the Safety Follow-up Visit will not be mandatory.
4. **Randomization:** An IRT system will be used for randomization. Randomization may be done up to 3 days prior to Day 1. During the Safety run-in, enrollment will be staggered with no more than 1 new subject treated per week, per treatment arm. Thereafter, a decision to further stagger combination enrollment will be made by the SRC and will be based on emergent safety data.

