20. **Shedding/clearance:** For subjects in the Safety Run-in at US sites only: urine, rectal swab, oral swab, and whole blood will be collected pre-CRS-207 dose, and at 6 hours, 18 to 24 hours, and Day 7 post-CRS-207 infusion end time on Cycle 1 and Cycle 2. **DO NOT use the central line for blood sample collection.** Additional assessments will be performed if results are positive for CRS-207 at the Day 7 time point. Samples will be sent to IHMA Central Laboratory.
21. **Tumor biopsies:** will be collected during the screening period (pre-first dose) and on Cycle 2 Day 15 (+7 days). Fine needle aspiration will not be acceptable. Samples will be sent to the Central Laboratory. Tumor biopsy should NOT be performed on the same day as CRS-207 or pembrolizumab administration. If additional biopsies are performed by Investigator for standard of care during the course of study, a sample should be retained for Sponsor research evaluation.
22. **Tumor evaluations:** will be performed using CT with contrast of the abdomen and pelvis (or MRI in case of contrast dye allergy) within 28 days prior to treatment, and repeated every 9 weeks (± 7 days) after initiation of study drug using the same assessment technique. Subjects who discontinue treatment for reasons other than PD should continue to have their disease assessed by CT every 9 weeks (± 7 days) until the start of a new anticancer therapy, documented PD, death, withdrawal of consent, or the end of study, whichever occurs first. Data from any standard of care CT scans may also be collected for tumor evaluation.

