23. **CRS-207:** will be administered on Day 2 of each cycle via IV infusion over approximately 1 hour (no in-line IV filter should be used). After Cycle 6, CRS-207 will be administered every six weeks, at even numbered visits (Cycle 8, Cycle 10, etc.) Study Medical Monitor must be notified for dose delays as noted in Section 4.3.1. Before each CRS-207 infusion, subjects will be pre-medicated with acetaminophen and saline will be given immediately before and after infusion with CRS-207 ([Section 5.5.2.1](#)). Subjects will be observed for at least 4 hours after each infusion. Subjects who are not stable enough to be released at 4 hours after infusion should continue to be monitored until stable. Presence of fever alone does not indicate subject is not clinically stable. Document the time subject becomes stable in the medical records. **To avoid inadvertent contamination of a central line (e.g. infusion ports, PICC lines), DO NOT administer CRS-207 or saline through a central line during infusion or for 4 days following infusion. DO NOT flush the central line for any reason during and for 4 days after CRS-207 infusion.**
24. **Epacadostat:** Epacadostat will be administered orally starting on Day 3 and BID thereafter. Tablets will be taken at the assigned dose in the morning and evening, approximately 12 hours apart. Epacadostat will be administered in clinic on Cycle 2 Day 1 and Day 2 in order to collect pre-dose blood sample for PK. Epacadostat dosing does not apply to CRS-207/pembro arm.
25. **Epacadostat Diary:** At each visit, provide a dosing diary and instructions on recording each dose of epacadostat. Collect unused epacadostat and review completed dosing diary with subject at following visit.
26. **Antibiotics:** A 7-day course of antibiotics will be administered at the EOT visit AFTER blood has been collected for CRS-207 culture to ensure clearance of CRS-207. Antibiotic regimen must be completed prior to initiation of any other cancer-related therapy. Subjects with a central line port will receive 1 dose of IV antibiotics followed by 6 days of oral antibiotics; all other subjects will receive 7 days of oral antibiotics (refer to [Section 5.6.3](#)). Site personal will contact the subject by to confirm compliance with the antibiotic treatment and document in source and CRFs.
27. **Pembrolizumab:** will be administered on Day 1 of each cycle via IV infusion over 30 minutes (-5/+10 minutes).

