5 STUDY TREATMENTS

5.1 Treatment Arms

Subjects will be assigned or randomized to the following treatment arms described in Table 5.

Table 5 ADU-CL-11 Treatment Cycles by Arm

Phase	Arm	Dose ¹ / Route	Treatment Cycle
1	CRS-207	CRS-207: 1×10^9 CFU by IV infusion over ~ 1 hour	CRS-207: Day 1 of each cycle (Cycles 1-6); Q6W thereafter
1	CRS-207/ IDO	CRS-207: 1×10^9 CFU by IV infusion over ~ 1 hour IDO: 100 mg or 300 mg BID Oral	CRS-207: Day 1 of each cycle (Cycles 1-6); Q6W thereafter IDO: BID starting Cycle 1 Day 2
2	CRS-207/ Pembro/ IDO	Pembro: 200 mg by IV infusion over 30 min CRS-207: 1×10^9 CFU by IV infusion over ~ 1 hour IDO: 300 mg Oral BID ¹	Pembro: Day 1 of each cycle CRS-207: Day 2 of each cycle (Cycles 1-6); Q6W thereafter IDO: BID starting Cycle 1 Day 3
2	CRS-207/ Pembro	Pembro: 200 mg by IV infusion over 30 min CRS-207: 1×10^9 CFU by IV infusion over ~ 1 hour	Pembro: Day 1 of each cycle CRS-207: Day 2 of each cycle (Cycles 1-6); Q6W thereafter

BID = twice daily; CFU = colony-forming units; IDO = epacadostat; IV = intravenous; pembro = pembrolizumab; Q6W = once every 6 weeks
¹ RP2D of epacadostat based on Phase 1 dose-evaluation parameters and determined by the SRC; the Phase 2 dose may be further adjusted during Phase 2 Safety Run-in

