8.1. Adverse Events

Treatment emergent adverse events (TEAEs) are defined as all events that occur from the time of first study drug administration until 30 days following the last dose of study drug or initiation of subsequent cancer-related therapy, whichever occurs first. TEAEs are assessed for severity using the NCI-CTCAE v. 4.0, relationship to each therapy, and seriousness. For Phase 1 data, infusion-related reactions (IRRs) are those which: have an onset date on or one day after the date of a CRS-207 administration; have been identified as related to CRS-207; and are coded to the following specific preferred terms: dyspnoea, chills, decreased appetite, fatigue, headache, hives, hypersensitivity, hypotension, hypoxia, influenza like illness, infusion related reaction, myalgia, nausea, pain, presyncope, pyrexia, rash, and vomiting. Phase 2 IRRs are identified by the investigator using the appropriate eCRF field.

A summary of TEAEs will be produced, including counts and percentages of subjects with any incidences of: TEAEs, CTCAE Grade 3 or higher TEAEs, TEAEs related to any study treatment, CTCAE Grade 3 or higher TEAEs related to any study treatment, serious adverse events (SAEs), SAEs related to any study treatment, TEAEs leading to study drug discontinuation, CRS-207 infusion related reactions, and fatal TEAEs.

Sponsor: Aduro Biotech, Inc.
Protocol Number: ADU-CL-11
Version and Date: Version 1.0, 03MAY2018

A separate summary of AEs identified as CRS-207 IRRs will include the number of infusions received by subjects, the number of subjects having an IRR, total number of IRRs per subject, maximum IRR grade, and dose modifications resulting from IRRs.

Adverse events will be coded based on the Medical Dictionary for Regulatory Affairs (MedDRA) version 18.1 or higher, for reporting by system organ class (SOC) and preferred term (PT) in descending order of overall incidence for the type of event reported. Within these summaries, TEAEs will be sorted for each subject by PT and severity; subjects will be counted once within a PT based on their TEAE having maximum severity.

Summaries of AEs by SOC and PT will include the following types of events:

- TEAEs;
- TEAEs related to any study treatment (Definitely Related, Probably Related, or Possibly Related);
- CTCAE Grade 3 or higher TEAEs;
- CTCAE Grade 3 or higher TEAEs related to any study treatment;
- CRS-207 infusion-related reactions;
- SAEs;
- SAEs related to any study treatment;

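### Section 5.5.2.1 allows release 2 hours after second and later CRS-207 infusions, while both schedules of events require 4 hours after every infusion.

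*Protocol*

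**What the plan says.** Protocol Section 5.5.2.1, under pre-medication and post-infusion observation, requires subjects to stay in the clinic for "at least 4 hours after the first CRS-207 infusion and at least 2 hours following each subsequent infusion". It adds that they are released once judged clinically stable and that vital signs are taken hourly during post-infusion follow-up.

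The Phase 2 schedule says otherwise. Table 1 footnote 23 reads "Subjects will be observed for at least 4 hours after each infusion", then "Subjects who are not stable enough to be released at 4 hours after infusion should continue to be monitored until stable". The Phase 1 schedule (Appendix F footnote 24) carries the same two sentences.

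The blood-pressure bullet later in Section 5.5.2.1 describes small drops "necessitating additional IV fluids during the 4 hour observation period". It does not limit that period to the first infusion.

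**The concern.** The protocol gives two different safety minimums for the same procedure. A site working from Section 5.5.2.1 can discharge a stable subject at 2 hours after the second infusion onward. A site working from either schedule cannot. The same discharge is compliant under one text and a deviation under the other.

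The shorter minimum removes part of the 4-hour period to which the protocol itself attaches blood-pressure drops needing up to 1 or 2 L of extra IV fluid. Two features make later infusions worth watching:

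- **Epacadostat overlap.** In the Phase 2 triple arm Table 5 has "IDO: BID starting Cycle 1 Day 3", the day after the first CRS-207 dose; the Phase 1 combination has the same one-day lag. Cycle 2 is therefore the first CRS-207 infusion given on top of epacadostat, and DLT evaluation covers Cycle 1 only (Section 5.3).
- **Fewer follow-up visits.** A visit on the day after CRS-207 is scheduled only in Cycles 1 and 2. Section 5.5.2.1 reports that some subjects were slightly hypotensive at 24 hours, on arriving for such a visit.

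**Working it through.** **The texts side by side**

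| Source | Applies to | After first infusion | After each later infusion |
|---|---|---|---|
| Section 5.5.2.1 | no phase stated | 4 h | 2 h |
| Table 1 footnote 23 | Phase 2 | 4 h | 4 h |
| Appendix F footnote 24 | Phase 1 | 4 h | 4 h |

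Three readings might reconcile them, and none does.

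1. *A difference between phases.* Section 5.5.2.1 has no phase qualifier, and both phase-specific schedules say 4 hours.
2. *The footnotes mean the first infusion only.* They refer to each infusion, and they treat 4 hours as the point at which release is first considered.
3. *A precedence rule.* Section 6 says assessments follow the Schedule of Events but does not say that it overrides other text. Section 9.8 sends the reader to Section 5.5.2.1 for vital signs during infusion. The two footnotes also cite Section 5.5.2.1, for pre-medication and saline.

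The stability condition does not close the gap either. A subject who is stable at 2 hours meets Section 5.5.2.1 and still falls short of the schedule.

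**Size of the gap**

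Per later infusion: 4 h − 2 h = 2 h. With hourly vital signs, that is 2 sets instead of 4.

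For a subject receiving k infusions, all at a site using the shorter minimum, the total is 2 × (k − 1) hours:

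- k = 2: 2 × 1 = 2 h
- k = 4: 2 × 3 = 6 h
- k = 6 (Cycles 1 to 6): 2 × 5 = 10 h

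The documents do not give k, so these are illustrations. Some subjects have shedding samples "at 6 hours, 18 to 24 hours, and Day 7 post-CRS-207 infusion end time on Cycle 1 and Cycle 2" (Table 1 footnote 20, for US sites in the Safety Run-in; Appendix F footnote 20 has a similar rule for Phase 1). The 6-hour sample already covers Cycle 2 for them, leaving Cycles 3 to 6: 4 × 2 = 8 h.

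**Time to the next scheduled visit (Phase 2, CRS-207 on Day 2)**

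| Cycle | Next scheduled visit | Interval |
|---|---|---|
| 1–2 | Day 3 | 3 − 2 = 1 day |
| 3–4 | Day 8 | 8 − 2 = 6 days |
| 5–6 | next cycle Day 1 (Day 22) | 22 − 2 = 20 days |

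Table 1 footnote 1 qualifies the last row: "At Cycle 5 and beyond, additional clinic visits between administrations of pembrolizumab and CRS-207 will be conducted based on" the investigator's discretion and clinical indication. The 20 days is therefore the scheduled interval, and extra visits are possible.

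**Effect on the safety analysis**

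SAP Section 8.1 defines Phase 1 infusion-related reactions partly as events that "have an onset date on or one day after the date of a CRS-207 administration". Phase 2 reactions are those the investigator marks on the eCRF. Neither definition depends on hours spent in clinic, so the observation window changes how an event might be noticed but not how it is classified.

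**The case against.** Both rules are minimums, so a site that always observes for 4 hours satisfies all three texts. Section 5.5.2.1 permits release at 2 hours only for a stable subject, and Section 6 points sites towards the schedule, which has the stricter figure. Site practice may also be set by a study reference manual that is not available here. These points show how a careful site would stay compliant. They do not supply a precedence rule, and a site may still reasonably follow Section 5.5.2.1.

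The supporting argument has real limits:

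- **The two features do not coincide.** Epacadostat first overlaps CRS-207 in Cycle 2, which has a next-day visit. The long intervals begin in Cycles 3 and 5, when the subject has already received the combination.
- **Phase 1 has other cover.** Epacadostat recipients have PK samples up to 6 hours after the morning epacadostat dose on Cycle 2 Day 1, the CRS-207 day (Appendix F footnote 19). They are likely to be on site for longer anyway.
- **Two arms are outside the epacadostat point.** It does not apply to CRS-207 alone or to CRS-207/pembrolizumab.
- **The evidence of harm is thin.** The blood-pressure drops are called small, with no onset time and no split between first and later infusions. Nothing shows that events occurred between hours 2 and 4 after a later infusion.
- **Shedding cover is narrower than it looks.** Section 9.7.8 restricts sampling to select US centers, so the 8-hour bound applies to fewer subjects.
- **Little exposure remained.** SAP Section 3.5 records the December 2017 decision to stop development, with all but 2 subjects through their end-of-treatment visit by 12 January 2018.

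All of this stands and limits the weight of the point. None of it removes the contradiction.

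**Conclusion.** The concern holds. For every CRS-207 infusion after the first, the current protocol gives minimums of both 2 and 4 hours, in both phases, with nothing to decide between them. The weight of the text favors 4 hours: two schedules and the blood-pressure bullet support it, and one sentence supports 2.

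The 10-hour figure assumes six infusions and use of the shorter minimum each time. It measures clinic time, not risk. The inconsistency should be corrected because it concerns the minimum monitoring after a live-bacteria infusion and because it leaves compliance undefined. It does not bear on the ORR or PFS criteria, the sample size or the DLT definitions.

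**What to change.** In Section 5.5.2.1, replace the split minimum with a single minimum of 4 hours after every CRS-207 infusion, keeping the stability condition for release. That brings it into line with Table 1 footnote 23 and Appendix F footnote 24. If 2 hours is intended for later infusions, leave Section 5.5.2.1 as it is, amend both footnotes and the blood-pressure bullet's reference to a 4-hour period, and state the safety data that justify the shorter stay.

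The first option costs one sentence of protocol wording and up to 2 more clinic hours per later infusion, only at sites that had used the shorter minimum.
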